## 8.0 STATISTICAL CONSIDERATIONS

The primary objective is to determine the feasibility of partial breast irradiation after repeat breast-conserving surgery for an IBTR. Thirty patients will be enrolled for this study and we expect to finish the enrollment within 5 years. For the safety of patients, interim analyses will be performed after 6, 12, 18 and 24 patients have reached 3 months and 1 year post treatment period. The protocol will remain open to enrollment during the interim analyses. The trial will be stopped if:

- The 3 month adverse event rate is determined to be in excess of 10%.
- A one-year local recurrence rate is more than 5%.

Assume the probability of 3 month adverse event (or 1 year local recurrence) is  $p$ , allowable maximum adverse event rate (or 1 year local recurrence rate) is  $p_0$  and the type I error is  $\alpha$ . The early stopping rules are based on the following statistical hypothesis test:

$$H_0: p \leq p_0 \quad \text{vs} \quad H_A: p > p_0$$

Based on the exact probability of Binomial distribution, we will reject the null hypothesis (i.e. stop the trial) if we observe  $k$  or more adverse events (local recurrences), where

$$k = \min \left\{ l : \sum_{i=l}^n \binom{n}{i} p_0^i (1 - p_0)^{n-i} \leq \alpha / 2 \right\},$$

and  $n$  is the number of patients at the time of the interim analysis.

The trial will be stopped if the 3 month adverse event rate is in excess of 10%. The trial will also be stopped if the 1-year local recurrence rate is more than 5%. The following table is based on  $\alpha = 0.05$ .

Minimum number of adverse events during first 3 months to stop the trial	Minimum number of local recurrences during the first 1 year to stop the trial	Number of patients treated
3	2	6
4	3	12
5	4	18
6	5	24

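### Four of the eight printed stopping counts in Section 8.0 do not follow the stated binomial formula, and no single tail level generates the whole table

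*Combined protocol and SAP*

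**What the plan says.** Section 8.0 gives two conditions for stopping the trial: "The 3 month adverse event rate is determined to be in excess of 10" per cent, and "A one-year local recurrence rate is more than 5" per cent. It then makes them operational: "The early stopping rules are based on the following statistical hypothesis test", with a one-sided alternative that the true rate p exceeds the maximum p0. The rule reads "Based on the exact probability of Binomial distribution, we will reject the null hypothesis (i.e. stop the trial) if we observe" k or more events. Here k is the smallest count for which the exact binomial probability of that many events or more, at p0, is at most α/2.

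On timing, "interim analyses will be performed after 6, 12, 18 and 24 patients have reached 3 months and 1 year post treatment period", and "Thirty patients will be enrolled for this study".

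A table follows, described as based on α = 0.05. Its two columns are headed "Minimum number of adverse events during first 3 months to stop the trial" and "Minimum number of local recurrences during the first 1 year to stop the trial". At 6, 12, 18 and 24 patients they contain 3, 4, 5, 6 and 2, 3, 4, 5.

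The section does not say why α is halved, whether α belongs to a look, an endpoint or the whole trial, or whether the formula or the table governs if they differ.

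**The concern.** The table is presented as the output of the formula, so the two should agree in every cell. Where they differ, the protocol gives two answers to the same data. At 4 adverse events in 12 patients, 5 in 18 or 6 in 24, or at 2 recurrences in 6, the table stops the trial and the formula does not.

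These are the only numerical stopping rules in the plan, they are there for patient safety, and enrollment stays open while the interim analyses are done. A monitoring body should not have to settle which rule was meant after the count is known. The error rate is also at stake: the two sets of counts have different false-stop probabilities, and the plan reports neither.

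**Working it through.** **Inputs, all from Section 8.0.** p0 = 0.10 for 3-month adverse events and 0.05 for 1-year local recurrence; α = 0.05, so the tail limit is α/2 = 0.025; looks at n = 6, 12, 18, 24.

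**Step 1: tails at the printed counts.** The tail is P(X ≥ k) for X binomial (n, p0). Two examples:

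- Adverse events, n = 12, k = 4: 1 − (0.28243 + 0.37657 + 0.23013 + 0.08523) = 0.0256.
- Recurrence, n = 6, k = 2: 1 − (0.73509 + 0.23213) = 0.0328.

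| Endpoint | n | Printed k | Tail at printed k | Tail at k − 1 | k at level 0.025 | k at level 0.05 |
|---|---|---|---|---|---|---|
| Adverse events | 6 | 3 | 0.0159 | 0.1143 | 3 | 3 |
| Adverse events | 12 | 4 | **0.0256** | 0.1109 | 5 | 4 |
| Adverse events | 18 | 5 | **0.0282** | 0.0982 | 6 | 5 |
| Adverse events | 24 | 6 | **0.0277** | 0.0851 | 7 | 6 |
| Recurrence | 6 | 2 | **0.0328** | 0.2649 | 3 | 2 |
| Recurrence | 12 | 3 | 0.0196 | 0.1184 | 3 | 3 |
| Recurrence | 18 | 4 | 0.0109 | 0.0581 | 4 | 4 |
| Recurrence | 24 | 5 | 0.0060 | 0.0298 | 5 | 4 |

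The plan's figures are reproduced in four cells. The four bold tails exceed 0.025, and in each the printed count is one below what the formula gives.

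**Step 2: is there another level that works?** A level L reproduces a printed k only if tail(k) ≤ L < tail(k − 1).

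- Adverse-event column: 0.0282 ≤ L < 0.0851, so a range of levels works.
- Recurrence column: 2 at n = 6 needs L ≥ 0.0328, while 5 at n = 24 needs L < 0.0298. No level meets both.

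A level of 0.05 therefore matches seven of eight cells and fails on recurrence at n = 24, where it gives 4. Mid-p, strict-inequality, normal (with and without continuity correction) and Poisson versions at 0.025 and 0.05 were also tried. None reproduces all eight cells.

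**Step 3: false-stop probability over four looks.** The running event count is carried forward in blocks of 6 patients, with the probability of reaching k removed at each look, at p = p0. Combining the endpoints as 1 − (1 − a)(1 − b) assumes independence, which the documents do not address.

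| Counts used | Adverse events | Recurrence | Either |
|---|---|---|---|
| Printed table | 0.0557 | 0.0467 | 1 − 0.9443 × 0.9533 = 0.0998 |
| Level 0.025 (the formula): 3/5/6/7 and 3/3/4/5 | 0.0244 | 0.0252 | 1 − 0.9756 × 0.9748 = 0.049 |
| Level 0.05: 3/4/5/6 and 2/3/4/4 | 0.0557 | 0.0589 | 1 − 0.9443 × 0.9411 = 0.111 |

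Without the independence assumption, the printed table's figure for either endpoint lies between 0.056 (the larger of the two) and 0.102 (their sum).

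**Step 4: effect when the true rate is too high.** The plan gives no alternative rate. Assuming a true adverse-event rate of 20%, twice the maximum, the chance of stopping at one of the four looks is 42% by the table and 25% by the formula.

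**The case against.** The strongest reply is that little is wrong in practice. The table gives explicit integers under headings that say they stop the trial, so a monitor would naturally apply it and treat the formula as its derivation. Three of the four tails exceed 0.025 by small amounts (0.0006, 0.0032 and 0.0027); only 2 recurrences in 6 is clearly over, by 0.0078. All four departures favour earlier stopping, so the table is never less protective than the formula. These points stand and limit the consequences. They do not remove the contradiction, because the text does not say that the table prevails and the recurrence column follows from no single level.

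A reader might infer that the printed rule has about twice the stated type I error. The documents do not support that without qualification. Section 8.0 introduces α as the type I error of one test, written for adverse events or, alternatively, recurrence. If 0.05 is meant for each endpoint over all looks, 5.6% and 4.7% are close to nominal. The doubling appears only if 0.05 covers both rules together (about 10.0%), or if α/2 = 0.025 is the cumulative allowance for each rule. Look by look it does not hold: the offending tails are 3% to 31% above 0.025.

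A reader might also infer that α/2 is simply a misprint for α. That explains seven cells but not the eighth.

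**Conclusion.** The inconsistency is real and is a matter of arithmetic: four of eight counts break the stated definition, each by one event and toward earlier stopping, and no common exact tail level yields the table. This part rests only on figures printed in Section 8.0. It should be corrected, because a stopping rule must give one answer for a given count.

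The effect on type I error is conditional. Relative to the formula, the printed table roughly doubles the cumulative false-stop probability (5.6% against 2.4%, 4.7% against 2.5%, about 10.0% against 4.9%). Whether it exceeds what was intended depends on a scope for α that the protocol leaves open. The combined figures assume independent endpoints, and all figures are for true rates exactly at 10% and 5%.

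**What to change.** In Section 8.0, reconcile the formula and the table so that one tail level generates all eight counts. State whether α applies to each look, each endpoint or the whole trial, and report the cumulative false-stop probabilities of the chosen counts. For reference:

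- Level 0.025 gives 2.4% (adverse events), 2.5% (recurrence) and 4.9% (either), and changes four table cells.
- Level 0.05 gives 5.6%, 5.9% and 11.1%, and changes the formula and one table cell.

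Which set applies is for the sponsor to decide; neither is recommended here. The cost is a small edit to one section. The downside is that the error the plan then states may look less favourable than the present α = 0.05.

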##### **5.1 Surgery**

- 5.1.1 Patients will undergo excisional biopsy or needle localization removal of the tumor.
- 5.1.2 Patients with margins < 2 mm undergo re-excision of the biopsy cavity.
- 5.1.3 For patients undergoing IORT, the skin around the excision site will be dissected and small skin flaps will be raised. The breast tissue is then loosely sutured so that the lateral margins are brought into apposition. The applicator will then be positioned to encompass the entire tumor bed with a 1 cm margin. After radiation has been delivered, sutures will be removed and the tumor bed will be closed in the typical fashion.

5.2 **Radiation Therapy** – Consultation via presentation at our multi-disciplinary breast conference between the surgeon, radiation oncologist and medical oncologist will take place to determine suitability for undergoing partial breast radiation and a recommendation will be made as to which modality is best suited for the patient. Clinical characteristics, including but not

limited to, distance of tumor from skin, patient's ability to tolerate another surgical procedure, patient's ability to come into the radiation department twice daily for treatment, will be considered in making this decision. All patients will be seen in consultation by the radiation oncologist prior to enrollment.

5.2.1 Intraoperative Radiation:

5.2.1a Applicator selection should allow for treatment of the tumor bed with a 1 cm radial margin.

5.2.1b Dosimetry on all applicators should be available to the radiation oncologist upon request in the operating room.

5.2.1c Energy of electrons should be such that the tumor cavity with a 1 cm margin will be covered by the 90% line. *The energy of the electrons will be at the discretion of the radiation oncologist and determined at the time of treatment to ensure proper coverage of the tumor cavity.*

5.2.1d A dose of 21 Gy will be prescribed to the 90% isodose line.

5.3.1 MammoSite® Brachytherapy:

5.3.1a Applicator Placement:

5.3.1a1 The MammoSite® applicator may be placed either at the time of surgery or in a separate procedure using ultrasound guidance after surgery. The MammoSite® applicator should be selected to best fit the cavity created by the surgical removal of the tumor.

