## 7.0 STUDY PARAMETERS

Study Parameters	Pre-Treatment	Follow-up
H&P/clinical evaluation	X	1 month after RT & Q3mos for one year, then annually for 5 years.
Mammogram	X	Ipsilateral breast 6 mos after dx, bilateral annually
CXR	X	Annually x 5 years
CT chest/abdomen/pelvis	X	If clinically indicated
Bone Scan	X	If clinically indicated
Cosmetic Evaluation/QOL assessment	X	1 month after RT & Q3mos for one year, and at 5 years.
Skin Assessment		Last day of RT
Breast MRI		If clinically indicated

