Safety analysis will be performed on all patients enrolled in the study. The incidence and its confidence interval of 3 month adverse events and 1 year local recurrences will be estimated. The time to local recurrence is calculated from the date of completion of radiation. Data for patients who remain free of local disease are censored as of date when the last follow-up information is obtained. At the end of the study, the cumulative local recurrence rate will be estimated by Kaplan-Meier method (46) for all patients (intend-to-treat) and 5-year recurrence rate will be then obtained and compared with those in the literature. The overall incidence and its confidence interval of acute complications following lumpectomy will be estimated. Also, we will estimate the overall incidence and the degree of fibrosis as defined on four-level scale of cosmetic outcome in appendix I.

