## **9.0 RECORDS TO BE KEPT**

At time of registration – Patient consent form, signed eligibility checklist and registration card.

Following breast conservation surgery for the second time, prior to beginning breast re-radiation, the cosmetic results of breast conservation will be assessed. Appendix I should be used. The same will be used to reassess the patient during radiation therapy, at one month post-radiation therapy, and every three months thereafter for one year, followed bi-annually for the remainder of the 5 year follow-up.

Follow-up Form - at time of disease response assessment, every three months during the first year and every 6 months thereafter for 5 years.

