## APPENDIX I

### COSMETIC GUIDELINES

**Patient #:** \_\_\_\_\_

Following breast conservation surgery, prior to beginning breast re-radiation, the cosmetic results of breast conservation will be assessed using these guidelines. The same guidelines will be used to reassess the patient during radiation therapy, at one month post-radiation therapy, and every three months thereafter for one year, then biannually for a total of 5 years.

Circle the number next to the word that best describes the cosmetic result.

1. EXCELLENT: When compared to the untreated breast or the original appearance of the treated breast, there is minimal or no difference in the size or shape of the treated breast. The way the breast feels (its texture) is the same or slightly different. There may be thickening, scar tissue, or fluid accumulation within the breast but not enough to change the appearance.
2. GOOD: There is mild asymmetry between the breasts, which means that there is some acceptable difference in the size or shape of the treated breast as compared to the opposite breast or the appearance of the breast before treatment. There may be some mild reddening or darkening of the breast. The thickening or scar tissue within the breast causes a mild change in its shape or size.
3. FAIR: Moderate deformity of the breast, with an obvious difference in the shape and size of the treated breast. This change involves  $\frac{1}{4}$  or less of the breast. There can be moderate thickening or scar tissue of the skin and the breast, and there may be obvious color changes.
4. POOR: Marked change in the appearance of the treated breast involving more than  $\frac{1}{4}$  of the breast tissue. The skin change may be obvious and detract from the appearance. Severe scarring and thickening of the breast, which clearly alters its appearance may be present. In retrospect, the breast may have been better treated by a mastectomy.

Code a response for each of the following items:

1. None
2. Yes, seen on close observation
3. Yes, seen on casual observation

\_\_\_\_\_ skin telangiectasia

\_\_\_\_\_ skin atrophy

\_\_\_\_\_ hyperpigmentation

\_\_\_\_\_ erythema

\_\_\_\_\_ fibrosis

\_\_\_\_\_ skin dimpling or indentation

\_\_\_\_\_ other significant treatment effects

specify: \_\_\_\_\_

During radiation therapy the patient will be evaluated weekly by the radiation oncologist. The following scale will be used to classify the acute skin reactions during treatment:

1. no change noted

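### Section 8 takes fibrosis from the four-level cosmesis scale, where no level means absence of fibrosis; the three-level fibrosis item on the same form should be used, and three assessment times need repair

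*Combined protocol and SAP*

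**What the plan says.** **Fibrosis.** Section 8.0 will estimate "the overall incidence and the degree of fibrosis as defined on four-level scale of cosmetic outcome in appendix I". The four-level scale in Appendix I is introduced by "Circle the number next to the word that best describes the cosmetic result" and runs from Excellent to Poor. Of the Excellent level it says "There may be thickening, scar tissue, or fluid accumulation within the breast but not enough to change the appearance"; of the Fair level, "There can be moderate thickening or scar tissue of the skin and the breast". Lower on the same form, fibrosis is one of seven items, each coded 1 (none), 2 ("Yes, seen on close observation") or 3 (visible on casual observation).

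**Cosmesis.** Cosmetic outcome with the different techniques is objective 2.2 and, as rated by the physicians, endpoint 6.2. In Section 8.0 the four-level scale appears only as the definition of fibrosis.

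**Baseline.** Section 9.0 states: "Following breast conservation surgery for the second time, prior to beginning breast re-radiation, the cosmetic results of breast conservation will be assessed". Appendix I says the same. For IORT, Section 5.1.3 states: "After radiation has been delivered, sutures will be removed and the tumor bed will be closed in the typical fashion". The Section 7.0 table also marks a pre-treatment cosmetic/QOL assessment, with no distinction by technique.

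**Acute skin.** Appendix I has a seven-level scale for reactions during treatment, with weekly evaluation while radiation is given. Section 7.0 places the skin assessment on the final day of radiation.

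**Schedule.** Section 7.0 sets follow-up cosmesis ratings at "1 month after RT & Q3mos for one year, and at 5 years". Section 9.0 and Appendix I have them biannually from the end of year 1 to year 5.

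**The concern.** The analysis text names a scale that was built for another purpose. A woman can have an excellent cosmetic result with palpable or faintly visible scarring, and a fair one because of lost volume or colour change. If the statistician follows Section 8.0 literally, the reported fibrosis rate is a cosmesis rate under another name, and the planned cosmetic endpoint gets no estimate of its own.

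The assessment times raise a related difficulty. They suit a course of radiation that starts days after surgery. They do not suit a single fraction given while the wound is open. All these women have already had surgery and whole-breast radiation, so a later rating is hard to interpret without a starting point defined in the same way for both techniques.

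**Working it through.** No sample size, power or error rate is involved, so the check is a comparison of texts. It assumes that thickening and scar tissue in the cosmesis wording refer to what the form elsewhere calls fibrosis; the documents give no definition.

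**1. What each cosmesis level says about scarring.**

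| Level | Scarring or thickening | What else decides the level |
|---|---|---|
| 1 Excellent | allowed, if appearance is unchanged | size, shape, texture |
| 2 Good | mild effect on shape or size | mild asymmetry, mild colour change |
| 3 Fair | moderate, possible but not required | obvious difference in shape and size, colour |
| 4 Poor | severe, possible but not required | marked change in over a quarter of the breast |

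**2. Can any cut-off recover incidence?** Take three women whom the form permits:
- A: cosmesis 1, fibrosis item 2 (slight scarring, appearance unchanged).
- B: cosmesis 3 because of volume or colour, fibrosis item 1.
- C: cosmesis 4 because of marked change without scarring, fibrosis item 1.

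| Rule for fibrosis present | A (has it) | B (does not) | C (does not) |
|---|---|---|---|
| levels 2 to 4 | missed | wrongly counted | wrongly counted |
| levels 3 to 4 | missed | wrongly counted | wrongly counted |
| level 4 | missed | correct | wrongly counted |
| levels 1 to 4 | counted | wrongly counted | wrongly counted |

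The last rule gives 100% by construction. No rule classifies all three correctly. Degree fails in the same way, since B and C score worse than A. The three-level item classifies all three correctly.

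**3. Size.** Section 8.0 plans 30 patients, so each misclassified woman shifts incidence by 1/30 = 3.3 percentage points. Women like A push it down; women like B and C push it up. The documents give no joint distribution of the two items, so the net error cannot be computed.

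**4. Baseline under IORT.** Radiation precedes closure (Section 5.1.3). When lumpectomy and IORT are one operation, there is therefore no time after surgery and before radiation at which to rate the breast. Section 10.0 lets a woman who has already had a lumpectomy return to the operating room for IORT; for her the time point exists. It also exists for MammoSite, which starts 3 to 7 days after implant (Section 5.3.1c1). The Section 7.0 pre-treatment rating is available for everyone, but the table does not say whether it comes before or after lumpectomy.

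**5. Acute skin under IORT.** With a single fraction, the last day of radiation is the day of surgery and no weekly visit falls during treatment. With MammoSite, the scale is scored during or at the end of a course of several days. If reactions take days to appear (a clinical assumption; the documents give no onset time), the scale can register them after MammoSite but hardly after IORT. This reads the Section 7.0 skin row as the occasion for the seven-level scale, which the table does not state.

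**6. Cosmesis ratings after year 1.** Section 7.0: one, at 5 years. Section 9.0 and Appendix I, read as six-monthly: (5 − 1) × 2 = 8. Read as every two years: 4 / 2 = 2. Section 9.0 has its own follow-up form six-monthly after year 1, which favours eight without settling it.

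**The case against.** The strongest reply is that the fibrosis fault is a loose cross-reference. The four levels do carry a rough gradient of scarring, the dedicated item is on the same page, no data are lost, and one sentence before analysis cures it. Most of that stands. The gradient is real but confounded, and it has no zero, so it cannot yield an incidence. That the cure is easy is a reason to apply it now.

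A reader might infer more than the documents support, in four ways:
- **That IORT patients have no baseline.** Section 7.0 schedules a pre-treatment rating for all, and some IORT patients will have had an earlier lumpectomy. Only the post-surgery rating in same-operation IORT is unobtainable, and the documents do not give the share of such patients.
- **That IORT patients have no usable skin assessment.** Appendix I codes erythema, hyperpigmentation, atrophy, telangiectasia and other effects at 1 month and every three months to one year, for both techniques. The gap is confined to the seven-level scale.
- **That IORT would look free of acute reactions in a formal comparison.** Section 8.0 plans no test between techniques, and the technique follows clinical suitability and patient choice. The risk lies in setting the descriptive results side by side on that one scale.
- **That the cosmesis and toxicity results are invalid.** The physician and patient ratings, wound healing, complications and the 3-month adverse event rate do not depend on these faults.

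It is also fair to say that Section 8.0 names feasibility as primary, so these are secondary results, and that its silence on the baseline does not rule out using it.

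**Conclusion.** The fibrosis analysis is wrong as written: the stated rule cannot give a valid incidence, and its grading of degree is confounded with other cosmetic change. The error is 3.3 percentage points per misclassified woman out of 30, in an unknown net direction. It is fully avoidable, because the right item is already collected. Cosmetic outcome, objective 2.2, has no estimate of its own in Section 8.0.

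The secondary faults are narrower. Change from a post-surgery baseline is unavailable for same-operation IORT. Comparison of techniques on the seven-level skin scale is unsound as scheduled, given the onset assumption above. The number of cosmesis ratings after year 1 is one in Section 7.0 and about eight elsewhere if biannual means six-monthly. None of this reaches the recurrence, adverse event or complication analyses. The plan should be changed, but the trial's main results do not hang on it.

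**What to change.** 1. **Section 8.0, fibrosis.** Estimate it from the three-level Appendix I item: incidence as code 2 or 3 with an exact 95% confidence interval, degree as the distribution of the three codes.
2. **Section 8.0, cosmesis.** Report the four-level scale as its own outcome: percent good or excellent with an exact 95% confidence interval, described by technique without a test. Name the visits in advance; year 1 and year 5 are common to Section 7.0 and to the six-monthly reading of Section 9.0 and Appendix I.
3. **Baseline.** Use the Section 7.0 pre-treatment rating as the common baseline and flag whether it was taken before or after lumpectomy. Keep the post-surgery rating wherever it can be obtained. Where the baseline precedes lumpectomy, say in the report that change includes the effect of the second excision.
4. **Acute skin.** Score the seven-level scale for everyone at the 1-month visit as well. Otherwise, state that the techniques will not be compared on it.
5. **Schedule.** Reconcile the cosmesis times after year 1 in Section 7.0, Section 9.0 and Appendix I, and say what biannual means.

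The cost is wording in Sections 7.0 to 9.0 and Appendix I (which now limits the seven-level scale to treatment), plus that scale at a visit already scheduled. No added patients or visits are needed for items 1 to 4. The lumpectomy flag can be set from the dated form and the surgery date.
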